**Table 2-4 High/Moderate/Low intensity statin therapy**

	High intensity	Moderate intensity	Low intensity
Statin name and dose/day	Atorvastatin 40 mg Rosuvastatin 20 mg	Atorvastatin $\geq$ 10 and < 40 mg Rosuvastatin $\geq$ 5 and < 20 mg Simvastatin 20 mg Pitavastatin 1-4 mg	Atorvastatin < 10 mg Rosuvastatin < 5 mg Simvastatin $\leq$ 10 mg Pravastatin $\leq$ 20 mg Fluvastatin $\leq$ 60 mg

Respecting reference 2018 AHA/ACA classification but taking into account the eventuality that some study subjects may be on doses falling between the consensus categories.

New or changed lipid-modifying therapy after baseline using the same categories as above will be summarized by treatment group.

Prior medications and other concomitant medications will be summarized by treatment group according to the Anatomical Therapeutic Chemical (ATC) classification system. Significant non-drug therapies (surgical and medical procedures) will be summarized by treatment group, according to the SOC and PT in the MedDRA dictionary.

## 2.5 Analysis of the primary objective

The analysis for the primary objective will be performed when all participants completed the Day 180 visit.

### 2.5.1 Primary endpoint

The analysis set used for the primary efficacy analysis will be the FAS.

The primary estimand is defined in [Section 1.3](#). The corresponding endpoint, i.e. primary analysis variable, is the percentage change in LDL-C from baseline to Day 180. The treatment effect (summary measure) of the primary estimand is the difference in mean percentage change from baseline to Day 180 between different inclisiran sodium dose groups and the placebo group.

### 2.5.2 Statistical hypothesis, model, and method of analysis

The primary objective of this study is to evaluate the effect of inclisiran compared to placebo in terms of percentage change from baseline in LDL-C to Day 180. The global statistical hypotheses that will be tested are as follows:

- $H_0: \mu_i - \mu_0 = 0$  for  $i=1,2,3$  versus  $H_a: \mu_i - \mu_0 < 0$  for at least  $i=1,2,3$

Where  $\mu_0$  is the mean percentage change in LDL-C from baseline to Day 180 in placebo group, and  $\mu_1, \mu_2, \mu_3$  are the mean percentage changes in LDL-C from baseline to Day 180 in inclisiran sodium 100mg, 200mg and 300mg group respectively.

An MMRM (Mixed-effect Model with Repeated Measurement) will be used as the primary analysis model, with treatment group, visits, interaction between visits and treatment groups and current use of statins or other lipid-modifying therapies as fixed effects and baseline LDL-C as a continuous covariate. Further details can be found in [Section 5.4.1](#).

The significance level of the hypothesis test is 0.025 using one-sided test. To control the overall type-one error rate, Dunnett's test (one step) will be used on the above statistical model to provide adjusted p-values. In addition, point estimate and 95% confidence interval will be presented for the difference between inclisiran and placebo groups. Also the p-value (before and after multiplicity adjustment) will also be provided.

The primary objective will be achieved if the null hypothesis is rejected.

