6.3.2 Treatment assignment, randomization

At Day 1 (baseline), all eligible participants will be randomized via Interactive Response Technology (IRT) to one of the treatment arms. The investigator or his/her delegate will contact the IRT after confirming that the participant fulfills all the inclusion/exclusion criteria. The IRT will assign a randomization number to the participant, which will be used to link the participant to a treatment arm and will specify a unique medication number for the first package of study treatment to be dispensed to the participant.

The randomization numbers will be generated using the following procedure to ensure that treatment assignment is unbiased and concealed from participants and investigator staff. A participant randomization list will be produced by the IRT provider using a validated system

that automates the assignment of participant numbers to a randomization numbers. These randomization numbers are linked to the different treatment code, which in turn are linked to medication numbers. A separate medication list will be produced by or under the responsibility of Novartis Global Clinical Supply (GCS) using a validated system that automates the random assignment of medication numbers to packs containing the study treatment.

Randomization will be stratified by LDL-C at screening visit (≥ 130 mg/dL or < 130 mg/dL), current use of statins or other lipid-modifying therapies (Yes or No), [REDACTED]

[REDACTED] otherwise the randomization ratio will be 2:2:1:1.

The randomization scheme for participants will be reviewed and approved by a member of the Randomization Office.

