12.8.1 Primary endpoint(s)

Approximately 308 participants will be randomized by the IRT system: 100 participants for inclisiran sodium dose groups 200 mg and 300 mg; plus 54 participants in the placebo group and inclisiran sodium dose group 100 mg. Randomization will be stratified by current use of statins or other lipid-modifying therapies, LDL-C category at screening, [REDACTED].

The sample size assumption was based on the observed results from a previously completed Phase II Dose Finding Study (ORION-1). The difference in mean percentage change from

baseline between the active dose groups and the placebo group for LDL-C at Day 180 is expected to be >30% with a standard deviation of approximately 20%.

The sample size of 308 will provide more than 90% power to detect a 30% reduction of LDL-C levels in at least one inclisiran sodium dose group compared to the placebo. Dunnett's test is used in order to control the family-wise type I error rate at a significance level of alpha=0.025 (one-sided test). The calculation is done using PASS 11 software.

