The stratification factors LDL-C category at screening and current use of statins or other lipid-modifying therapies [REDACTED] will be included in subgroup analysis where appropriate.

Additional analysis may be conducted to evaluate the impact of COVID-19 pandemic on participants finishing or discontinuing the Day 180 visit assessments and completing or discontinuing the End of Study visit..

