### 3 Sample size calculation

Approximately 308 participants will be randomized by the IRT system: 100 participants for inclisiran sodium dose groups 200 mg and 300 mg; plus 54 participants in the placebo group and inclisiran sodium dose group 100 mg. Randomization will be stratified by current use of statins or other lipid-modifying therapies, LDL-C category at screening, [REDACTED].

The sample size assumption was based on the observed results from a previously completed Phase II Dose Finding Study (ORION-1). The difference in mean percentage change from baseline between the active dose groups and the placebo group for LDL-C at Day 180 is expected to be >30% with a standard deviation of approximately 20%.

The sample size of 308 will provide more than 90% power to detect a 30% reduction of LDL-C levels in at least one inclisiran sodium dose group compared to the placebo. Dunnett's test is used in order to control the family-wise type I error rate at a significance level of alpha=0.025 (one-sided test). [REDACTED].

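### The listed primary MMRM has no visible term for a further, redacted randomisation factor, although allocation appears not to be uniform; any resulting bias is conditional and small

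*SAP*

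**What the plan says.** **Randomisation.** Protocol 12.8.1 and SAP 3 state: "Randomization will be stratified by current use of statins or other lipid-modifying therapies, LDL-C category at screening", followed by blacked-out text. Protocol 6.3.2 gives the categories (screening LDL-C split at 130 mg/dL; lipid-modifying therapy, LMT, yes or no). More blacked-out text follows and runs into the ratio sentence, which ends "otherwise the randomization ratio will be 2:2:1:1". The planned arms are 100 each for 300 mg and 200 mg, and 54 each for 100 mg and placebo, 308 in total.

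**Primary model.** Protocol 12.4.2 and SAP 2.5.2 name the same terms: treatment, visit, treatment by visit, statin/LMT use and baseline LDL-C. The SAP words the last two as "current use of statins or other lipid-modifying therapies as fixed effects and baseline LDL-C as a continuous covariate". SAP 2.5.2 refers to SAP 5.4.1 for details, and that section is blacked out. The key secondary endpoints use the same method.

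**Testing.** "The significance level of the hypothesis test is 0.025 using one-sided test", and "Dunnett's test (one step) will be used on the above statistical model to provide adjusted p-values".

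**Subgroups.** SAP 2.1 says that screening LDL-C category and statin/LMT use "will be included in subgroup analysis where appropriate". Table 2.2 splits baseline LDL-C at its median and has no row for the 130 mg/dL screening stratum. SAP 2.3.1 already defines that grouping for the baseline table.

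**The concern.** Of the factors used to randomise, only statin/LMT use enters the model directly. Screening LDL-C enters indirectly, through continuous baseline LDL-C. No visible term represents the redacted factor.

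With a constant allocation ratio this would matter little: leaving out a stratification factor costs some precision and tends to make the standard error conservative, but does not bias the treatment difference. It matters more when the ratio changes between strata. The arms then differ in stratum mix by design and not by chance. If the stratum also predicts the outcome, part of the stratum effect is counted as a treatment effect.

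Two things are at stake: the 200 mg and 300 mg differences from placebo, and the gradient between 100 mg and the higher doses. The gradient is relevant because Protocol 4.2 describes the study as a check on whether the optimal dose in Japanese participants matches that in non-Japanese participants.

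**Working it through.** **1. The plan's own figure.** SAP 3 says the difference "is expected to be >30% with a standard deviation of approximately 20" per cent, and "The sample size of 308 will provide more than 90% power to detect a 30% reduction of LDL-C levels" in at least one dose group. With SE = 20 × √(1/54 + 1/n):

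- 200 mg and 300 mg (n = 100): 20 × √(1/54 + 1/100) = 3.38
- 100 mg (n = 54): 20 × √(2/54) = 3.85

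The one-sided Dunnett critical value for three doses with 304 degrees of freedom is 2.336 (2,000,000 draws). A 30-point effect is 30/3.38 = 8.9 or 30/3.85 = 7.8 standard errors, so power exceeds 99.9% for every dose. The stated figure holds.

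**2. Is allocation uniform?** A uniform 2:2:1:1 split of 308 gives 308/3 = 102.7 in each larger arm and 308/6 = 51.3 in each smaller arm, not 100 and 54. Assume that an excepted stratum of size x is allocated 1:1:1:1 and the rest 2:2:1:1. Then x/4 + (308 − x)/3 = 100, so x/12 = 2.667 and x = 32. Check: 8 + 276/3 = 100 and 8 + 276/6 = 54.

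The placebo volumes in Protocol Table 3-1 (12/21/21) add little. The assumed mix gives 46/5 + 8/3 = 11.9 and 2 × 46/5 + 8/3 = 21.1. Splitting 54 in proportion to 54:100:100 gives 11.5/21.3/21.3, which fits almost as well.

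**3. Difference in stratum mix.** Under this assumption the stratum is 8/100 = 8.0% of the 200 mg and 300 mg arms, and 8/54 = 14.8% of the placebo and 100 mg arms. The gap is 6.8 points for the higher doses and zero for 100 mg. Other assumed ratios in the excepted stratum also reproduce the arm sizes: 3:3:2:2 (x = 80) gives a gap of 5.6 points, 1:1:2:2 (x = 16) gives 7.2, and 0:0:1:1 (x = 8) gives 7.4.

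**4. Bias.** Let D be the difference in percentage LDL-C change between the stratum and the rest that remains after the planned covariates, taken as equal in all arms. Then bias = D × (8/54 − 8/100) = 0.068 × D. For the ratio of bias to SE, the SD is √(20² + D²p(1 − p)) with p = 32/308. Family-wise error is computed with no true effect at any dose.

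| Assumed D | Bias, 200/300 mg (points) | Bias/SE | Error if stratum responds worse | Error if stratum responds better |
|---|---|---|---|---|
| 0 | 0 | 0 | 0.025 | 0.025 |
| 5 | 0.34 | 0.10 | 0.030 | 0.021 |
| 10 | 0.68 | 0.20 | 0.035 | 0.018 |
| 20 | 1.36 | 0.39 | 0.050 | 0.015 |

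Bias for 100 mg is zero in every row. If the stratum responds worse, the benefit of 200 mg and 300 mg is overstated; if better, understated.

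**5. Does adding the factor remove it?** This was simulated with 4,000 trials per scenario, a true effect of −30, and a single-visit ANCOVA with treatment and baseline LDL-C standing in for the planned model. Statin/LMT use, repeated visits and dropout were not simulated. Results for 300 mg:

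| Model | D = 0 | D = 10 | D = 20 |
|---|---|---|---|
| Treatment and baseline LDL-C | −29.9 | −30.6 | −31.4 |
| + screening LDL-C category | −29.9 | −30.6 | −31.4 |
| + excepted stratum | −29.9 | −30.0 | −30.1 |

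The mean SE was 3.38, 3.41 and 3.53 in the first row, and 3.39 throughout in the last. The LDL-C category changes nothing once continuous baseline LDL-C is in the model. The stratum term removes the bias without loss of precision.

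**The case against.** The strongest objection is that the decisive facts are blacked out. The public text does not show which factor sets the ratio, what the other ratio is, or whether the factor predicts LDL-C change. If the ratio varies by statin/LMT use, the model already adjusts for it. If it varies by screening LDL-C, baseline LDL-C covers most of it. Eight participants per arm would also suit an equal-sized sampling subset with no bearing on response, in which case the bias is nil. SAP 5.4.1 might hold a further term. The simulation assumes the stratum and its effect, so it confirms the formula and says nothing about the trial itself.

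This stands, and it is why the point is conditional. It does not remove the point. The term lists in Protocol 12.4.2 and SAP 2.5.2 are unredacted and agree with each other. If SAP 5.4.1 contains the missing factor, those lists should say so.

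It is also fair that the last SAP versions (17 and 18 October 2022) are marked as written after the primary analysis, and that Protocol 6.4 unblinds most sponsor staff after the Day 180 lock. Replacing the primary model at that stage would be a post-unblinding change. On Table 2.2, SAP 2.1 leaves room through its qualifier about appropriateness, so the missing row is a small mismatch.

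**Conclusion.** The point holds in conditional form. The listed model has no visible term for the redacted factor, and non-uniform allocation is a fair inference from the ratio wording together with the arm sizes. If the ratio depends on a factor absent from the model, and that factor is prognostic, the 200 mg and 300 mg differences are biased by 0.34 to 1.36 points for D of 5 to 20. Across the other assumed ratios the range is 0.056 × 5 = 0.28 to 0.074 × 20 = 1.48 points. The 100 mg difference is unaffected, so the gradient from 100 mg to the higher doses shifts by the same amount.

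This rests on assumed values of D, an assumed exception to the ratio, planned arm sizes and no dropout. It does not threaten the detection of a 30-point effect.

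A reader might infer more than the documents support:

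- That a bias is established. It is not: both conditions lie behind redaction.
- That two factors are ignored. Screening LDL-C is largely represented by continuous baseline LDL-C.
- That the redacted factor is HeFH, because the roughly 30 planned HeFH participants are close to 32. Nothing visible identifies it.
- That the standard errors are materially wrong. At D = 10 they are 3.41 and 3.39 without and with the factor.

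Nor does this point give grounds for a baseline-by-visit interaction.

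**What to change.** 1. In Protocol 12.4.2 and SAP 2.5.2, include every randomisation factor, in particular the one that drives the allocation ratio, as a fixed effect in the primary and key secondary MMRM. If a factor is left out on purpose, state why.
2. For SAP versions dated after the primary analysis, leave the primary model as it is. Report the model with all randomisation factors as a sensitivity analysis, labelled as added after the primary analysis, and set its dose differences beside the primary ones.
3. Add a screening LDL-C row (<130, ≥130 mg/dL) to Table 2.2 so that it agrees with SAP 2.1.

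The cost is minor: one or two model terms, or one extra analysis, and one subgroup row. The stratum assignments come from the randomisation system, and SAP 2.3.1 already defines the LDL-C grouping.

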### **2.5.3 Handling of missing values/censoring/discontinuations**

The MMRM model implicitly imputes missing data under a missing at random (MAR) assumption and results are valid under this MAR assumption. Patients who have at least one post-baseline are included in the MMRM analysis. This includes not only the patients who have completed Day 180 visit, but also those who discontinue from study treatment early (although only able to contribute to a partial time profile). This is under the assumption that dropouts would follow the similar data pattern like other patients who complete the treatment period in the same treatment group, as if they had not discontinued from the study treatment.

Patients who discontinue from study treatment early will remain in the study and follow the procedures described in protocol Section 9.1. All collected data after discontinuation from study treatment will be used in the analysis based on the treatment policy strategy in [Section 1.3](#).

The other potential intercurrent events could be death, which considering its expected small number of occurrences with the short follow-up period planned and being consistent with the approach in the other phase II and III studies, will be treated the same way as for the other missing data.

### **2.5.4 Supportive/Sensitivity analyses**

The following sensitivity analysis will be performed for the primary estimand, to assess the robustness of the estimation in the presence of deviations from the assumptions specified in the primary analysis:

- MMRM analysis with multiple imputation using a control-based pattern mixture model (PMM)

The control-based pattern mixture model (PMM) will be used to explore the possibility of missing data being missing not at random. This approach will utilize placebo data for monotone missing inclisiran treatment data. The details are described in [Section 5.4.2](#).

## **2.6 Analysis of the key secondary objective**

### **2.6.1 Key secondary endpoint**

The key secondary efficacy endpoints of this study are the following:

- Percentage change in PCSK9 from baseline to Day 180

- Absolute change in LDL-C from baseline to Day 180

### **2.6.2 Statistical hypothesis, model, and method of analysis**

The key secondary efficacy endpoints will be analyzed using the same methods as for the primary efficacy endpoint.

Descriptive statistics on percentage change from baseline in LDL-C and PCSK9 and absolute change from baseline in LDL-C will include number of participants (n), mean, standard deviation, median and interquartile range [first and third quartiles], minimum and maximum.

The two-sided 95% confidence interval for difference will be provided for continuous variables. Nominal p-values will be provided when applicable.

For displaying the results, figures of LDL-C and PCSK9 (absolute mean by visit, percentage change from baseline by visit, absolute mean change from baseline by visit) and waterfall plot of LDL-C (percentage change and absolute change from Baseline to Day 180) will be used.

### **2.6.3 Handling of missing values/censoring/discontinuations**

Same approach as for primary analysis will be applied.

## **2.7 Analysis of other secondary efficacy objective(s)**

### **2.7.1 Secondary endpoints**

The other secondary efficacy objectives of this study are to evaluate the effect of inclisiran on the following:

- Percentage change in PCSK9 levels from baseline to Days 14, 30, 60, 90, 104, 120, and 150
- Percentage change in LDL-C from baseline to Days 14, 30, 60, 90, 104, 120, and 150
- Proportion of participants in each group with LDL-C greater than 80% of the baseline value at Day 180 ([Appendix 5.5](#))
- Percentage change in other lipids, lipoproteins, apolipoproteins from baseline to Days 14, 30, 60, 90, 104, 120, 150, and 180
- Proportion of participants in each group with greater or equal to 50% LDL-C reduction from baseline at Days 14, 30, 60, 90, 104, 120, 150, and 180
- Individual responsiveness defined as the number of participants reaching LDL-C levels of <25 mg/dL, <50 mg/dL, <70 mg/dL, and <100 mg/dL at Days 14, 30, 60, 90, 104, 120, 150, and 180
- Proportion of participants in each group who attain Japanese lipid modification targets specified by JAS-2017 and JAS-2022 guidelines ([Appendix 5.5](#)) for their level of cardiovascular risk at Day 180

### **2.7.2 Statistical hypothesis, model, and method of analysis**

- For other secondary endpoints, only the descriptive statistics by treatment group will be presented. The two-sided 95% confidence interval for the proportion will be provided using the exact method of Clopper and Pearson.

### **2.7.3 Handling of missing values/censoring/discontinuations**

Missing values for other parameters will not be imputed. Discontinuations are treated the same as for the primary analysis.

## **2.8 Safety analyses**

The safety objectives of this study are to evaluate the safety and tolerability profile of inclisiran. For all safety analyses, the safety set will be used. All listings and tables will be presented by treatment group.

Safety summaries (tables, figures) include only treatment-emergent events (events started after the first dose of study medication or events present prior to start of double-blind treatment but increased in severity based on preferred term) with the exception of baseline data which will also be summarized where appropriate (e.g. change from baseline summaries). In addition, a separate summary for death including on treatment and post treatment deaths will be provided. In particular, summary tables for AEs will summarize only treatment emergent AEs.

The primary analysis after all participants discontinued before Day 180 visit or have finished Day 180 visit assessments will be conducted.

### **2.8.1 Adverse events (AEs)**

All information obtained on adverse events will be displayed by treatment group and participant.

The MedDRA dictionary will be used for coding AEs. An AE (classified as preferred term) occurring during the double-blind treatment period will be counted as a TEAE either if it is not present at baseline or if it is present at baseline but increased in severity during the treatment period.

The number (and percentage) of participants with TEAEs (events started after the first dose of study medication or events present prior to start of double-blind treatment but increased in severity based on preferred term) will be summarized in the following ways:

- by treatment, primary system organ class and preferred term.
- by treatment, primary system organ class, preferred term and maximum severity
- by treatment, primary system organ class and preferred term for treatment emergent AEs leading to study drug discontinuation
- by treatment, primary system organ class and preferred term for treatment emergent AEs related to study drug.

Separate summaries will be provided for death and serious adverse events (SAEs). The overview summary table (TEAEs, Severe AEs, SAEs, Fatal SAEs, AEs leading to discontinuation and respective treatment-related) will be provided.

A participant with multiple adverse events within a primary system organ class is only counted once towards the total of the primary system organ class.

Listings will also be generated for deaths, SAEs, TEAEs and AEs leading to discontinuation.

